9.4 Statistical Analyses

9.4.1 General Approach

Descriptive statistics for continuous variables will include the mean, standard deviation, N, median, and range in the form of a minimum and maximum. Categorical data will be summarized using percentages and the count (numerator) and N (denominator) used to calculate the percentage. All formal testing will be done at the 0.05 level of significance unless otherwise stated.

The details of the statistical analysis can be found in the JEWEL SAP.

9.4.2 Additional Analyses

All Adverse Device Effects and device-related SAEs will be tabulated and presented. A summary of all AEs and SAEs, including the proportion of subjects experiencing an AE or SAE, along with duration, severity, and relatedness to the Jewel will also be presented to ensure that device safety performance is adequately summarized.

As a measure of compliance, daily wear time will be calculated for all subjects enrolled in JEWEL.

Details regarding the analysis of Jewel System Compliance calculations, the Detection of Ventricular Arrhythmias, and QOL will be outlined in the SAP.

9.4.3 Baseline Descriptive Statistics

Baseline characteristics of the enrolled population will be presented. These characteristics include demographics such as gender, age, sex, medical history, and co-morbidities including COVID status. These characteristics will be summarized as outlined in Section 9.4.1.

9.4.4 Planned Interim Analyses

A single interim analysis will be performed after 179 or more subjects have completed their prescription wear time. This analysis will be used to stop the trial early for both safety and effectiveness. The Type I error rate for this analysis will be set to 0.03.

There is another planned analysis once 100 subjects have completed their prescription wear time, which will be performed to support application for CE mark. The data will be summarized descriptively and no formal hypothesis testing will be done at this point, so no adjustment for the Type I error rate is necessary. The results of the 100 subject interim analysis will not be used to terminate the IDE trial prior to completion of enrollment and subject follow up.

9.4.5 Sub-Group Analyses

Since sub-groups are not powered, a formal comparison to the rate of 2.0% per 100 patient months will not be done. The rate of inappropriate shock will be analyzed separately for males and females, COVID positive versus COVID negative, as well as for individuals with a Body Mass Index of ≤25 and >25. Details of the sub-group analysis can be found in the SAP.

9.4.6 Tabulation of Individual Subject Data

Individual subject data will be listed by measure and time point. We will describe subject weartime and any notable events, specifically inappropriate shocks and/or successful conversions.

9.4.7 Study Site Poolability

Site poolability will be assessed using an Rx2 table where each site is a row in the table and the two columns are "number of subjects experiencing an inappropriate shock" and "number of subjects free from inappropriate shocks." Details of the analysis will be outlined in the SAP.

9.4.8 Handling Missing Data

It is expected that most subjects will wear the device between 40 and 90 days. Wear time and handling of missing data will be described in detail the SAP.

10. SUPPORTING DOCUMENTATION AND OPERATIONAL CONSIDERATIONS

10.1 Regulatory, Ethical, and Study Oversight Considerations

10.1.1 Informed Consent Process

10.1.1.1 Consent/Assent and Other Informational Documents Provided to Subjects

Consent forms describing in detail the Jewel, study visits/calls, and risks are given to the patient. Written documentation of informed consent is required prior to enrollment in the study.

10.1.1.2 Consent Procedures and Documentation

Informed consent is a process initiated prior to the individual's agreeing to participate in the study and continues throughout the individual's study participation. Consent forms will be IRB-approved and the patient will be asked to read and review the document. The Investigator will explain the research study to the patient and answer any questions that may arise. A verbal explanation will be provided in terms suited to the patient's comprehension of the purposes, procedures, and potential risks of the study, and of their rights as research subjects. Patients will have the opportunity to carefully review the written consent form and ask questions prior to signing. The patients will have the opportunity to discuss the study with their family or surrogates or think about it prior to agreeing to participate. The patient must sign the informed consent document prior to any procedures being done specifically for the study. Patients must be informed that participation is voluntary and that they may withdraw from the study at any time, without prejudice. A copy of the fully executed informed consent document will be given to the subjects for their records. The informed consent process will be conducted and documented in the subject's medical record (including the date and time), and the informed consent form signed, before the subject undergoes any study-specific procedures. The rights and welfare of the subjects will be protected by emphasizing to them that the quality of their medical care will not be adversely affected if they decline to participate in the study.

10.1.2 Study Discontinuation and Closure

The study may be temporarily suspended or prematurely terminated if there is sufficient reasonable cause. Suspension/termination may occur at the site-level or at the study-level. Written notification documenting the reasons for study suspension or termination will be provided by the suspending or terminating party to study Investigators, the Sponsor, and regulatory authorities, as appropriate. If the study is prematurely terminated or suspended, the PI at each site will promptly inform the IRB, and will provide the reason(s) for the termination or suspension. Subjects will be contacted, as applicable, and be informed of any changes to study visit schedule.

Circumstances that may warrant termination or suspension include, but are not limited to:

- Determination of unexpected, significant, or unacceptable risk to subjects
- Demonstration of effectiveness that would warrant stopping
- Insufficient compliance to protocol requirements
- Data that are not sufficiently complete and/or evaluable
- Determination that the primary endpoint has been met
- Determination of futility

Following suspension, study activities may resume once concerns regarding safety, protocol compliance, and/or data quality are addressed and satisfy the sponsor and/or Food and Drug Administration (FDA), as appropriate.

10.1.3 Confidentiality and Privacy

Subject confidentiality and privacy is strictly held in trust by the participating Investigators, their site staff, and the Sponsor. Confidentiality is extended to cover all clinical, demographic, and contact information relating to patients. The study protocol, documentation, data, and all other information generated will be held in strict confidence. No information concerning the study or the data will be released to any unauthorized third party without prior written approval of the Sponsor.

All research activities, including subject training, will be conducted in as private a setting as possible.

The study monitor, other authorized Sponsor representatives, representatives of the IRB and/or regulatory agencies, may inspect all documents and records required to be maintained by the PI, including but not limited to medical records (office, clinic, or hospital), and pharmacy records for subjects. The site will permit access to such records.

The subject's contact information will be securely stored in Sponsor's database(s) and at each clinical site for internal use throughout the study. At the completion of the study, all records will continue to be kept in a secure location for as long a period as dictated by the reviewing IRB, Institutional policies, or Sponsor requirements.

For purposes of study conduct, specifically including shipping and receiving of investigational product directly to subjects, Sponsor representatives may find themselves in possession of subject contact information. This contact information will be held in the strictest confidence and will only be used to fulfill requests from the subjects for training and assistance and for provision and receipt of Jewel study supplies.

Subject device data will be transmitted to and stored by the Sponsor. These data will not include the subject's contact or identifying information. Individual subjects and their device data will be identified by a unique study identification number. Device data stored directly on the Jewel will be retrieved from Jewel by trained Sponsor personnel. These data will be identified by device serial number which will be used to link the data to a specific subject. Study data entry and study management systems used by sites and by the Sponsor and their research staff and designees will be secured and password protected. At the completion of the study, all study databases will be deidentified and archived by the Sponsor or their representative.

10.1.4 Future Use of Stored Data

Data collected for this study will be analyzed and stored by Element Science. Permission to transmit data to Element Science will be included in the informed consent.

10.1.6 Safety Oversight

All delivered shocks, both appropriate and inappropriate, will be reviewed and adjudicated by a CEC. The CEC will meet regularly, and may meet on-demand, as needed.

[contact]

Safety oversight will be provided under the direction of a DSMB composed of individuals with appropriate expertise, including interventional cardiology and/or electrophysiology. Members of the DSMB will be independent from the study conduct and free of conflict of interest, or measures will be in place to minimize perceived conflict of interest. The DSMB will meet regularly to assess safety and study conduct. The DSMB will operate under the rules of an approved charter that will be written and reviewed at the organizational meeting of the DSMB. At that time, each data element that the DSMB will assess will be clearly defined. The DSMB will provide its input to the Sponsor.

10.1.7 Clinical Monitoring, Quality Assurance and Quality Control

Monitoring for this study will be performed by the Sponsor or their representative and will consist of a combination of on-site monitoring visits and centralized reviews of data on an ongoing basis. Before acceptance of the clinical data, the Sponsor will review the data entered on electronic case report forms (eCRFs) for completeness and adherence to the protocol based upon source documentation verification (SDV). Procedures to be followed and the data to be fully monitored to SDV will be described in detail in the Clinical Monitoring Plan (CMP). For example, all safety data and primary and secondary endpoint measures as defined by the protocol will be 100% monitored against the source data.

The Sponsor will qualify investigative sites through review of the adequacy of the subject population, facilities, equipment and resource needs of the study, and will familiarize the Investigator with the study protocol.

At the time of enrollment, the Sponsor will meet with the Investigator to ensure that subjects will be properly selected, consented, and enrolled, that the study protocol is thoroughly understood,

the method(s) surrounding clinical data collection and capture are understood, and to confirm the Investigators acceptance of her/his regulatory obligations.

Assigned Clinical Monitors of the Sponsor may visit the site(s) periodically during the study to perform SDV. Visits may also be performed remotely. The Investigator and Institution must guarantee direct access to all relevant medical records by designated monitors and regulatory authorities.

The study may be subject to a quality assurance audit by either the Sponsor or by regulatory authorities. It is important that the Investigator and the assigned authorized study personnel are available during monitoring visits and possible audits, and that sufficient time is dedicated to the process. The site will provide direct access to all trial related sites, source data/ documents, and reports, for monitoring and auditing by the Sponsor, and for inspection by local and regulatory authorities. In the event of a local or regulatory authority audit, the site is expected to immediately notify the Sponsor of the audit.

The Sponsor will be responsible for coordinating and conducting the handling of clinical study data. Procedures will be described in detail in the Data Management Plan and the Statistical Analysis Plan. Data quality control checks will be run on the database on a regular basis. Any missing data, anomalies, or questionable fields will be communicated to the site for clarification/resolution.

10.1.8 Data Handling and Record Keeping

Data Collection and Management Responsibilities

Case Report Form Data

All source documents should meet the ALCOA criteria (accurate, legible, contemporaneous / complete, original, and attributable) to ensure correct interpretation of data. Data recorded in the eCRF derived from source documents should be consistent with the data recorded on the source documents.

The Investigator is responsible for ensuring the quality and accuracy of the data reported. All data generated at the site deemed related to the clinical trial will be entered into an eCRF via an electronic data capture (EDC) system. eCRF data is the responsibility of the clinical trial staff at the site, at the discretion of the PI. Data related to Investigational Product accountability and data from Jewel that is entered in the EDC will be done via API (Application Programming Interface). The EDC will be 21 CFR Part 11-compliant, provided by the Sponsor. The EDC system will include password protection and internal quality checks, such as automatic range checks, to identify data that appear inconsistent, incomplete, or inaccurate. Clinical data will be entered directly into the EDC from the source documents, and within seven (7) days of data collection if possible.

Jewel Device Data

All Jewel devices will be collected by the Sponsor following the end of the prescription period or device use, and the electronic records will be extracted and archived as source data. Primary and secondary endpoint data will be collected from analysis and relevant CEC review of the source data. For each wear duration, the Jewel records the electrocardiogram, trans-thoracic impedance, defibrillation data, algorithm results for every time the shockable rhythm classification algorithm is run, all button presses and all alarms. Each of these data points are time stamped.

If a subject receives a delivered shock (either appropriate or inappropriate) a report of the 60 seconds preceding and 30 seconds following the shock will be provided to the Investigator.

It is anticipated that the Site and Sponsor may become aware of events of interest, but Jewel data are not available for the events due to mishandling, non-compliance with returning the device, inappropriate disposal, data overwriting, or data corruption. These events may include, for example, inappropriate shock delivery or appropriate shocks that may or may not have resulted in conversion of life-threatening VT or VF. Should any of these events of interest be reported by the subject or study site without the concurrent Jewel data available, the site shall provide the Sponsor and CEC with as much information regarding the event as possible. The CEC will review and adjudicate these situations on a case-by-case basis for inclusion in the endpoint analysis. Any such events will also be described.

As the Jewel collects some limited information on electrograms during wear-time, it is possible that cardiac events of interest may be captured by the Jewel. Data on incidental findings (i.e., arrhythmias not associated with a delivered or deferred shock) will not be provided to the investigation site team. However, if an event is adjudicated by the CEC and a cardiac rhythm of interest is observed, the CEC will inform the Investigator and provide the relevant supporting data.

Study Records Retention

Study documents should be retained for a minimum of two (2) years after the last approval of a marketing application or until at least two (2) years have elapsed since the formal discontinuation of clinical development of the Jewel. These documents should be retained for a longer period, however, if required by local regulations. No records will be destroyed without the written consent of the Sponsor. It is the responsibility of the Sponsor to inform the site when these documents no longer need to be retained.

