3.2 Endpoints

3.2.1 Primary Effectiveness Endpoint

To demonstrate an observed inappropriate shock rate of no more than 2.0 inappropriate shocks per 100 patient-months using a one-sided upper 97% confidence interval and >83% power at the interim analysis; and a 98% confidence interval and >98% power for the final analysis.

An inappropriate shock is defined as a shock delivered during a period where the study subject is not experiencing life threatening VT or VF. Only first inappropriate shocks will contribute the analysis of this endpoint. All inappropriate shocks will be reviewed and adjudicated by a Clinical Events Committee (CEC) and reported throughout the prescription period.

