3.2.3 Secondary Endpoints

The first secondary endpoint is to observe successful conversion of at least one shockable rhythm with a salvo of up to five (5) shocks.

A shock is considered appropriate if the shock is delivered during a period where the subject is experiencing VF or a VT that is considered "life threatening" as defined in the CEC Charter and as adjudicated by the CEC. If multiple successful conversions occur in a single subject, conversions will be counted as separate events only if the rhythm returned to a non-shockable rhythm between conversions (i.e. the Jewel returns to Monitor Mode). All successful conversions will be included in the secondary endpoint analysis. All appropriate shocks and attempted conversions will be reviewed and adjudicated by the CEC and reported.

The second secondary endpoint is to observe a compliance rate of subjects wearing the Jewel of greater than 14.1 average hours per day during a prescription wear period.

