3.1. Primary Analysis Population

All subjects with analyzable wear times following initial Jewel enrollment will be included in the analysis population for the primary effectiveness endpoint. Analyzable wear time is defined as beginning 12-hours after the date and time the first Jewel applied to the subject's body transitions to Monitor Mode to when the last Jewel worn by the subject transitioned to Off Body Mode. Periods of removal time as identified by timestamped transitions between modes, periods of removal time as attested to by a subject or health care provider and confirmed by electrocardiographic data, and periods of time in which there are missing data (e.g. due to unreturned or damaged devices) will be excluded.

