5.1. Primary Effectiveness Endpoints

All shocks during analyzable wear time will be recorded, centrally evaluated and adjudicated by the Clinical Events Committee (CEC), and reported.

The primary effectiveness endpoint is the rate of inappropriate shock. A one-sided upper 98% confidence limit will be calculated for the inappropriate shock rate per 100 patient-months at the final analysis. Specifically, an intercept-only Poisson regression model will be fit to the data. All wear times through the first inappropriate shock or through death or withdrawal or wear times for subjects without inappropriate shock, death, or withdrawal at the time of analysis will contribute to the Poisson regression model. The one-sided upper 98% confidence limit inappropriate shock rate will be calculated by taking the one-sided upper 98% confidence limit of the intercept parameter in the regression model. The null hypothesis will be rejected if the upper confidence limit on the inappropriate shock rate is less than 2.0.

The formal hypotheses are:

 H_0 : Inappropriate shock rate ≥ 2.0 per 100 patient-months H_a : Inappropriate shock rate < 2.0 per 100 patient-months

The analysis will be re-run on the per protocol analysis population if that population is different from the primary analysis population. Results of this analysis are strictly supportive.

Note that subjects experiencing an inappropriate shock will continue to be followed and accumulate wear time in order to collect data on the other endpoints of this trial.

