5.5. Interim Analyses

An interim analysis of the Primary Endpoints will be performed after 179 subjects or more have completed their prescription wear time. This analysis will be used to stop the trial early for both safety and effectiveness.

This interim analysis will be analyzed as described in Section 5.1 above, with the exception that a one-sided upper 97% confidence bound will be used. This effectively spends 0.03 alpha on the interim analysis, reserving 0.02 alpha for the final analysis. Splitting the overall alpha into two pieces that add up to the overall alpha is a recognized way of controlling the Type I error rate. This can be seen by calculating the probability of making a Type I error. First calculate the probability of not making a Type I error which is:

Prob(no Type I in interim analysis)*Prob(no Type I in final analysis)= 0.97*0.98=0.9506

The probability of making a Type I error is then one minus the probability of not making any Type I errors which is:

Prob(Type I error)= 1.0 - 0.9506 = 0.0494

This particular split in alpha also corresponds to using a cumulative error spending function of Jennison and Turnbull (2000) defined as:

$$E(t,\rho) = \begin{cases} 1 & if \quad t \ge 1 \\ t^{\rho} & if \ 0 < t < 1 \\ 0 & otherwise \end{cases}$$

where ρ is the power parameter (here ρ =1.059) and t is the information fraction at the time of the interim analysis (here t = 179/290). Given these values, the amount of alpha spent at the interim analysis is:

 $\alpha^* E(179/290, 1.059) = 0.05^*(179/290)^{1.059} = 0.02999$

The safety endpoint will also be tested at this interim analysis only if the primary effectiveness endpoint is achieved. The trial will only be stopped if both the primary effectiveness and primary safety endpoints are achieved.

There is another planned analysis when 100 subjects have completed their prescription wear time, which will be performed to support application for CE mark. The data will be summarized descriptively and no formal hypothesis testing will be done at this point, so no adjustment for Type I error rate is necessary. Once discussions with the Notified Body are concluded, this document will be updated with details regarding the analysis.

6. Handling of Missing Data

It is expected that most subjects will wear the device between 40 and 90 days. Subjects with missing wear times will not have their data imputed for the purpose of the primary endpoint analysis.

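### Protocol and SAP disagree on whether a reported shock without Jewel data enters the primary count, no default or sensitivity analysis is given, and one shock can decide the result

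*Protocol*

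**What the plan says.** Protocol 3.2.1 promises full adjudication: "All inappropriate shocks will be reviewed and adjudicated by a Clinical Events Committee (CEC) and reported throughout the prescription period". Protocol 10.1.8 (Jewel Device Data) then expects that some events will have no Jewel record because of mishandling, non-return, disposal, overwriting or corruption. It names "inappropriate shock delivery or appropriate shocks that may or may not have resulted in conversion of life-threatening VT or VF" among them. The site supplies what information it can, and for inclusion the rule is: "The CEC will review and adjudicate these situations on a case-by-case basis for inclusion in the endpoint analysis". The paragraph ends: "Any such events will also be described".

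The SAP does not carry this rule over. On analyzable wear time, SAP 3.1 states that "periods of time in which there are missing data (e.g. due to unreturned or damaged devices) will be excluded". SAP 5.1 defines the shocks of interest as follows: "All shocks during analyzable wear time will be recorded, centrally evaluated and adjudicated by the Clinical Events Committee (CEC), and reported". SAP section 6 adds: "Subjects with missing wear times will not have their data imputed for the purpose of the primary endpoint analysis". It says nothing on a shock whose rhythm cannot be classified.

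The first secondary endpoint (Protocol 3.2.3) is to "observe successful conversion of at least one shockable rhythm with a salvo of up to five (5) shocks". SAP 5.2 takes in every shockable episode met during the trial and does not restrict it to analyzable wear time. Protocol 9.1 and SAP 5.2 both say that this endpoint is not formally tested.

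**The concern.** The two documents give different answers to a simple question: does a reported shock with no device record count? Under the Protocol it counts if the CEC includes it. Under the SAP, taken literally, it lies in excluded time and does not count. Neither document gives a criterion, a default or a sensitivity analysis.

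The gap is not symmetric. A shock without data can leave the primary count, where events hurt the device, while a conversion without data can stay in the secondary count, where a single event is enough. In a single-arm, unblinded study judged against a fixed goal on a handful of events, the rule should be fixed before the data are seen.

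**Working it through.** **Inputs.** SAP 8: normal wear time, mean 2.5 months and SD 0.5; exponential time to first inappropriate shock; expected rate 0.37 per 100 subject-months; 0.5 events assigned to a study with none. SAP 5.1 and 5.5: success if the upper limit is below 2.0, with one-sided limits of 97% at 179 subjects and 98% at 290.

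**1. Reproduce the plan.** For an intercept-only Poisson model with d events in T months, the Wald upper limit is 100 × (d/T) × exp(z/√d), with z = 1.881 (97%) and 2.054 (98%). Simulating as in SAP 8 gives power of 97.9–98.0% at 290 (stated: about 98%) and 83.4–83.7% at 179 (stated: >83%). Both figures reproduce.

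**2. Pass limits at planned exposure.**

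| Look | T (months) | Events | Upper limit | Result |
|---|---|---|---|---|
| Final | 290 × 2.5 = 725 | 6 | 1.91 | pass |
| Final | 725 | 7 | 2.10 | fail |
| Interim | 179 × 2.5 = 447.5 | 3 | 1.986 | pass |
| Interim | 447.5 | 4 | 2.29 | fail |

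The exact Poisson limit gives the same cut-offs (1.85 and 2.04; 1.90 and 2.23). Three events at the interim is a narrow pass: it needs T of at least 150 × exp(1.881/√3) = 444.3 months.

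**3. Effect of one shock.** With 7 true shocks and one left out, the final limit is 1.91. It is 1.92 if that subject's 2.5 months go too (T = 722.5). Either way a fail becomes a pass. At the interim the same happens between 4 and 3.

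**4. False-pass risk if loss is tied to shocks.** The documents give no share of shocks without data, so 5%, 10% and 20% are assumptions. At a true rate of 2.0 the chance of a first shock per subject is about 1 − exp(−0.02 × 2.5) = 0.0488. If a share m of shocks is left out, the final false-pass risk is close to the binomial chance of at most 6 events in 290 with probability 0.0488 × (1 − m). The interim has no such shortcut, because 3 events pass only with enough exposure, so it is simulated.

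| Share left out | Final, binomial | Final, simulated | Interim, simulated |
|---|---|---|---|
| 0% | 1.1% | 1.2% | 1.4% |
| 5% | 1.8% | 1.7–1.8% | 1.7–1.9% |
| 10% | 2.8% | 2.5–2.9% | 2.4–2.8% |
| 20% | 6.3% | 6.1–6.5% | 4.3–4.6% |

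The nominal levels are 2% (final) and 3% (interim). The final level is passed only at roughly 10% or more. The interim level is still met at 10% and is passed at 20%.

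**5. The neutral case.** If 5%, 10% or 20% of subjects are lost regardless of shocks, and their wear time is removed as SAP 3.1 requires, the false-pass risk is about 0.9–1.1% at the final and 0.7–1.4% at the interim. There is no inflation.

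**6. How often it would matter at the design rate.** Expected shocks are 0.0037 × 725 = 2.7 (final) and 0.0037 × 447.5 = 1.7 (interim). The chance of exactly 7 at the final is about 1.4%, and of exactly 4 at the interim about 5.9%. A changed verdict also needs one of those shocks to be without data and left out.

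**The case against.** The plan has safeguards. Protocol 8.1.4 asks for immediate reporting of delivered shocks. Shock data go to the cloud through the App, or a sponsor representative visits the subject and downloads them, so retrieval does not wait for the device to come back. Protocol 10.1.8 has every event without data described, so an omission would be visible. At the design rate a changed verdict is unlikely. The CEC Charter, which is cited but not among the documents, may hold further rules. All of this stands and limits the size of the point. It does not settle which document governs the count, and a description does not enter the confidence limit that decides success.

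A reader might go further in three ways that the documents do not support.

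- *That Type I error is inflated as planned.* This needs loss linked to shocks and exclusion of every such shock. The 20% in Protocol 9.2 is a subject-level allowance for withdrawal, loss to follow-up and lost or damaged devices. It is not a rate of unreadable shocks.
- *That an undocumented rescue can be claimed as a success.* The site must supply what it has, Protocol 8.2.9 asks for source documents on clinical events that lead to care, and the CEC adjudicates. The accurate description is a conversion without device data.
- *That shocked subjects will discard the device, or that the CEC will lean towards the sponsor.* Nothing in the documents shows either.

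**Conclusion.** The point holds as a mismatch between Protocol 10.1.8 and SAP 3.1 and 5.1, with no default for an unclassifiable shock. It is worth correcting because one event can decide the primary result at either look. Under shock-linked loss with full exclusion, the final false-pass risk goes from about 1.2% to about 1.7–1.8%, 2.6–2.8% and 6.3% at the assumed 5%, 10% and 20%. At the interim it goes from about 1.4% to about 4.4% at 20%. Under neutral loss the effect is nil. The secondary endpoint is descriptive, so that half of the point concerns interpretation and has no Type I error consequence. The figures rest on the SAP 8 wear-time model and on assumed loss shares.

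**What to change.** 1. Reconcile Protocol 10.1.8 with SAP 3.1, 5.1 and 5.2, so that a reported delivered shock is not dropped because its device data are missing. State that the subject's exposure up to the shock is kept with it. SAP 3.1 and section 6 need a matching exception, with a named source for that exposure, such as the reported exchange dates.
2. Pre-specify an analysis, shown beside the primary result at both looks, in which every delivered shock without Jewel data counts as inappropriate unless another contemporaneous ECG shows life-threatening VT/VF. Say whether the conclusion changes.
3. Count a successful conversion only when a contemporaneous ECG, from the Jewel or elsewhere, documents both the rhythm and its conversion.

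The cost is a few sentences in the Protocol, SAP and CEC Charter. The downside is that a true VT/VF shock with lost data may count against the device in the second analysis. If one such shock were always added at the design rate, the chance of passing that analysis would be about 94–95% at the final instead of 98%. At the interim it would be about 65% instead of 83–84%: 0.507 (at most 1 true shock) plus about 0.54 of the 0.262 chance of 2 true shocks, since a total of 3 passes only with enough exposure. For this reason it is proposed as a companion analysis. Making the worst case the primary rule is debatable, because Protocol 3.2.1 defines an inappropriate shock by the rhythm.
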